#### 4.3.2 Secondary outcomes:

User acceptability

• Valve self-report questionnaire (Valve self-report questionnaire) *Quality of life* 

• EQ-5D-5L and Long-term Catheter Quality of Life Tool

URINARY CATHETER 'FILL AND FLUSH' VALVE:

SAFETY, EFFECTIVENESS, ACCEPTABILITY AND FEASIBILITY TRIAL Protocol Version 3.1 20/08/2019 - IRAS: 245818 - ERGO: 41448

## 5. CLINICAL INVESTIGATION DESIGN

This study a 'first in human' assessment of reliability, effectiveness, comfort and user acceptability with 16 long-term catheter users.

This study will be in one phase over 6 months, and compromise of 2 groups:

Group 1 (n=8)	Safety cohort (n=4)	Interim Safety review	(n=4)	
Group 2 (n=8)				(n=8)

Group 1- The valve will initially be tested in 8 participants who currently use a standard manual valve (without leg-bag). Such participants (and their bladders) will be accustomed to the filling and emptying of the bladder with an IDC in situ and therefore represent the most predictable and safest population on which to test the valve.

This first group will include a safety cohort of participants (n=4). All safety data will be reviewed from the initial 4 participants before further participants can undergo the study investigation. Review of the initial data will include an interim safety report submission to the Medicines and Healthcare products Regulatory Agency (MHRA) in line with the issued Notice of No Objection.

Once all relevant permissions to proceed have been granted, the valve will then be tested in the remainder of standard manual valve participants (n=4) to complete Group 1.

Group 2 - The valve will then be tested with participants (n=8) who currently use a drainage bag with free drainage in order to test the valve with people who are no longer accustomed to the process of filling and emptying the bladder (Group 2).

After use (in both groups), the valves will be examined microbiologically in the University of Southampton laboratory to detect bioburden and/or biofilm to ascertain a baseline for future studies.

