## 3.4 Risks and Benefits

It is hypothesised that the benefit of the valve is this could overcome the problems cited above by ensuring optimal bladder filling followed by swift urine drainage and flushing of the catheter and drainage bag lumen thereby also reducing the risk of biofilm formation and blockage.

The potential risk is that the valve will not open or will not fully drain the bladder. This risk will be mitigated by only recruiting participants who have bladder sensation and who can report any discomfort, by scanning the bladder hourly to check the volume of urine has not risen above acceptable levels and by removing the valve should any problems occur.

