#### 6.1.1 Definitions of Solicited AEs:

The adverse event (AE) most likely to occur in this study is bladder discomfort. This is a study outcome and therefore will not be reported. Other potential AEs are listed in Table 2. As with bladder discomfort these AEs will be recorded but not reported.

Relationship	Description
POSSIBLE	Urinary leakage
POSSIBLE	Bladder discomfort
POSSIBLE	Catheter blockage
POSSIBLE	Haematuria
POSSIBLE	Accidental Removal
Yes	Valve not opening

[figure not shown]
Table 2 Solicited Adverse Events (AEs)

6.1.2 Specific actions following Adverse Events:

Participant advised to stop using the valve:

- If symptoms suggest a urinary tract infection advise the participant to send a urine sample to their GP
- Participant reverts to usual form of urinary catheter
  - URINARY CATHETER 'FILL AND FLUSH' VALVE: SAFETY, EFFECTIVENESS, ACCEPTABILITY AND FEASIBILITY TRIAL Protocol Version 3.1 20/08/2019 - IRAS: 245818 - ERGO: 41448

• If symptom recurs, participant to be withdrawn

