#### 6.3 Safety Stopping Criteria

If none of the first 4 participants have successfully completed protocol (in either day 1 or day 2), the trial will be stopped.

In case of occurrence of an SAE considered to be at least possibly related to trial or in case of two severe or clinically significant AEs considered to be at least possibly related to the trial, the study will be halted. The trial will only be re-started following an internal review of safety.

Clinically significant adverse events are:

- Accidental dislodgement of urinary catheter during intervention.
- The requirement to change the urinary catheter.
- New bladder or pelvic pain not resolved by the removal of the valve.

URINARY CATHETER 'FILL AND FLUSH' VALVE: SAFETY, EFFECTIVENESS, ACCEPTABILITY AND FEASIBILITY TRIAL

Protocol Version 3.1 20/08/2019 - IRAS: 245818 - ERGO: 41448

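### No planned review of the full Group 1 data comes before Group 2, and non-openings managed as the protocol directs would not prompt one

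*Protocol*

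**What the plan says.** Section 5 orders exposure by expected risk. Manual-valve users come first because they "represent the most predictable and safest population on which to test the valve". Within that group there is a safety cohort of four, and "All safety data will be reviewed from the initial 4 participants before further participants can undergo the study investigation". This review includes an interim safety report to the regulator. Once permissions are in place, "the valve will then be tested in the remainder of standard manual valve participants (n=4) to complete Group 1". The next step is Group 2: "The valve will then be tested with participants (n=8) who currently use a drainage bag with free drainage". Section 5 describes these as people whose bladders have lost the habit of filling and emptying. It states no review, hold or first cohort at that step, and the section 5 table shows the interim review in the Group 1 row only.

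Section 6.3 has two trial-level rules.

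- **Completion rule:** "If none of the first 4 participants have successfully completed protocol (in either day 1 or day 2), the trial will be stopped".
- **Event-driven halt:** one SAE at least possibly related to the trial, or two severe or clinically significant AEs so related, halts the study until an internal safety review. This rule is not limited to a group. The clinically significant events are catheter dislodgement, a needed catheter change, and new pain that persists after the valve is removed.

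Section 3.4 names the main device hazard: "The potential risk is that the valve will not open or will not fully drain the bladder". Section 4.3.1 makes opening before capacity and residual volume primary outcomes under the label of safety. Table 2 in section 6.1.1 lists "Valve not opening" as a solicited AE. Such events are logged without onward reporting.

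**The concern.** The point of going from a safer group to a less predictable one is that the first group's results inform the decision to expose the second. Here the planned look uses half of Group 1. Results from the other four manual-valve users are collected, but the protocol does not say that anyone reviews them before Group 2 begins.

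The trial-level rules do not clearly fill that gap. The completion rule never looks beyond the first four participants. The halt depends on event types that do not name the hazard in section 3.4. Several Group 2 participants could have a valve that fails to open or leaves a large residual, each handled correctly at the bedside, without any rule asking the team to pause and look across participants.

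**Working it through.** **Cohort sizes.** Section 5 gives 4 (safety cohort) + 4 (rest of Group 1) + 8 (Group 2) = 16, which agrees with the stated sample size. The protocol gives no operating characteristics for either rule and no event rates, so every rate below is an assumption shown over a range. Participants are treated as independent.

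**Completion rule.** The trial stops only if 0 of 4 complete. With true completion rate p among manual-valve users, P(stop) = (1 − p)^4.

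- p = 10%: 0.9^4 = 65.6%
- p = 25%: 0.75^4 = 31.6%
- p = 50%: 0.5^4 = 6.25%
- p = 90%: 0.1^4 = 0.01%

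The rule catches a valve that almost never works. It passes one that fails in half of Group 1 with probability 93.75%.

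**What the planned review can exclude.** After 0 events in n participants, the one-sided 95% upper bound is 1 − 0.05^(1/n).

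- n = 4: 1 − 0.05^(1/4) = 52.7%
- n = 8: 1 − 0.05^(1/8) = 31.2%

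Using all of Group 1 narrows the bound noticeably. Both bounds describe manual-valve users. Neither is a direct estimate for free-drainage users.

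**Non-openings in Group 2.** Let q be the assumed proportion of Group 2 participants with at least one non-opening. Then P(two or more of 8) = 1 − (1 − q)^8 − 8q(1 − q)^7.

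- q = 10%: 1 − 0.4305 − 0.3826 = 18.7%
- q = 20%: 1 − 0.1678 − 0.3355 = 49.7%
- q = 30%: 1 − 0.0576 − 0.1977 = 74.5%
- q = 50%: 1 − 0.0039 − 0.0313 = 96.5% (expected number 8 × 0.5 = 4)

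**Would those non-openings trigger the halt?** Sections 5.6.1 and 5.6.2 direct that a valve that does not open is disconnected, the bladder drained, and that participant's testing ended. Set against section 6.3:

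- Non-opening and incomplete emptying are not on the clinically significant list.
- Discomfort that goes away once the valve is off falls outside the pain item on that list.
- Appendix A reserves the severe grade for incapacitating discomfort.

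A non-opening managed as directed therefore counts towards the halt only if it is graded severe, is judged serious, or comes with one of the listed events.

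**The case against.** A reader might infer that nothing in the protocol responds to valve failure in Group 2. The documents do not support that. Section 3.4 sets out hourly scanning, removal of the valve if problems occur, and recruitment limited to people with bladder sensation. Sections 5.6.1 and 5.6.2 end testing for anyone whose valve does not open, and section 5.6 applies the same process to both groups. What is missing is a trial-level look, not individual protection.

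A reader might also infer that Group 2 starts with no review at all. That goes too far as well. The review of the first four precedes every later participant, the halt runs throughout and leads to an internal review, and section 7.7 lets the investigators, steering committee or sponsor terminate at any time.

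Nor do Table 2 and section 6.3 contradict each other. One governs reporting and the other governs halting, solicited events are not exempt from the halt, and a non-opening graded severe would count.

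It is also fair to say that opening and residual volume are outcomes the study exists to observe, under close supervision, and that leaving them off the halt list can be defended. The documents give no reason to expect any particular non-opening rate in Group 2, or that it is several times the Group 1 rate. At 10%, two or more non-openings among eight would be the exception. Finally, the terms of the Notice of No Objection are not shown and may already require a further step.

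These points limit the concern but do not remove it. Stopping one participant does not tell the team whether to expose the next, and the protocol fixes its own review points without one between the groups.

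**Conclusion.** The point holds as a gap in staging. The only planned review and the completion rule rest on the first four manual-valve users, and no planned trial-level review of the full Group 1 data precedes Group 2. The halt continues in Group 2 but would usually miss non-openings and incomplete emptying that are managed as directed and not graded severe.

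The size depends on rates that the documents do not give. Over assumed Group 2 non-opening rates of 10% to 50%, the chance of two or more affected participants among eight runs from 18.7% to 96.5%. The completion rule offers little backstop, stopping with probability 6.25% at an assumed 50% completion rate in Group 1.

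It would be too strong to say that participants are unprotected or that the staged design is defeated. The gap merits a cheap improvement and does not show the trial to be unsafe as written.

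**What to change.** In sections 5 and 6.3, add one internal review of all Group 1 data before the first Group 2 participant is tested. It should cover valve opening, residual volume, discomfort, and all AEs including the solicited events in Table 2. Tabulate valve non-opening and residual volume at that review and at the existing review of the first four. State who conducts it. The criteria for proceeding are for the sponsor and clinical team to set, and any relevant conditions in the Notice of No Objection should be written into the protocol.

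The cost is a short pause and one more internal summary of data already collected, with no extra participants. The pause would be longer if a regulator submission were also required, as at the first review. A further look after the first Group 2 participants would be the first planned look at that population. It is optional and would add a second pause.

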#### 5.1 Setting:

This 'first in human' phase will take place in controlled conditions at the Southampton NIHR Clinical Research Facility (CRF) at University Hospital Southampton NHS Foundation Trust.

Some of the key safety measures in place include:

- The Southampton NIHR Clinical Research Facility (CRF) is located within University Hospital NHS Foundation Trust, adjacent to the acute medical and intensive care wards.
- Clinical nursing staff based in the NIHR CRF are Immediate Life Support (ILS) trained (with annual updates) as a minimum.

- Clinical staff based in the CRF attend an emergency scenario training session at least annually.
- Standard Operating Procedures (SOPs) are in place for managing common medical emergencies such as anaphylaxis, syncope etc.
- Emergency resuscitation trolleys are in place throughout the facility.

Southampton

- Emergency call bells are tested every three months to ensure that they are in working order, and a bi-weekly check of pull cords is conducted to make sure they are accessible and have not been tied up or moved out of reach.
- As a hospital ward, the NIHR CRF has full use of the 24 hour emergency response teams in case of a medical emergency.
- A hospital style bed will be provided.

Each participant will attend two visits (up to a maximum of 7 hours per day) at the CRF testing the valve.

Appropriate refreshments will be provided, and travel expenses will be reimbursed.

## 5.2 Equipment:

5.2.1 Trial Valves:

The trial valves will be provided sterile by the manufacturer Rainbow Medical Engineering Ltd. The valves and packaging will be labelled for clinical trial only with additional information as set out in the CIB. Three valves (one of each pressure variant) will be provided for each participant per day, plus 8 additional spare devices (= total of 24 per variant).

Each valve will be identified with a unique serial number, batch number and patient label set. All reference numbers will be recorded against participant study IDs on a reconciliation log.

Study teams will be trained on changing and/ or replacing trial valves as per study specific SOP.

5.2.2 Standard valves:

Each participant will be given a new valve of the type they usually use after testing is complete on each day. Therefore 16 standard (manual) valves will be required.

5.2.3 Drainage bags:

One drainage bag will be provided at the start of each day/testing period (16 in total).

5.2.4 Bladder scanner:

A new scanner will be purchased for study use.

5.2.5 Absorbent pads:

To protect participant's clothing from any leakage. One pad per participant visit (n=32)

## 5.3 Sample:

Sixteen men and women aged 18 or over who have a long-term indwelling urinary catheter in situ (urethral or suprapubic) and use either a manual valve or a drainage bag. Sixteen is anticipated to be a sufficient sample size to address the preliminary 'first in human' research questions on effectiveness, usability and acceptability.

## 5.4 Recruitment and consent:

We will recruit 16 long-term IDC users (8 who currently use a standard manual valve e.g. a 'flip-flo' – with or without an attached drainage bag- and 8 who use just a drainage bag).

#### 5.4.1 Recruitment Methods

Local GP practices will be invited to act as Participant Identification Centres (PIC) sites. This will supported by Wessex Clinical Research Network:

- PIC sites will be asked to search for long-term catheter users (including those who use valves and drainage bags or drainage bags only) and asked to identify potential participants using the eligibility criteria.
- PIC sites will then provide or send a letter of invitation containing an expression of interest form with a freepost return envelope to prospective participants.
- PIC sites will be provided with a flyer that includes a brief description of the study and contact details for the research team. This can to be provided to urinary catheter users or used as a poster.

If full recruitment numbers have not been achieved in the anticipated timelines:

• Local NHS sites may also be invited to act as Participant Identification Centres (PIC). All relevant sponsor, ethical and regulatory approvals will be sort prior to implementing this change.

#### 5.4.2 Patient Information Sheets

In each case, the potential recruits will be asked to contact the research team directly (providing their contact details) if they wish to find out more about the study. Potential participants will be sent a Participant Information Sheet (PIS). This will be followed up (no sooner than 24 hours after they have received the PIS) with a phone call to discuss the study, answer any questions and check eligibility.

#### 5.4.3 Confirmation from General Practitioner

Those who wish to participate, who have not been identified by their GP, will then be sent a form to obtain their written consent for the research team to contact their GP for a letter of confirmation of health status and potential eligibility to participate in study.

#### 5.4.4 Informed Consent Process

Participants will be required to give informed consent at the first visit to the Clinical Research Facility. The person who obtains the consent must be suitably qualified and experienced, check eligibility, and have been authorised to do so by the Chief/Principal Investigator.

The participant must personally sign and date the latest approved version of the informed consent form before any clinical investigation specific procedures are performed. It will be clearly stated that the participant is free to withdraw from the clinical investigation at any time for any reason without prejudice to future care, and with no obligation to give the reason for withdrawal.

A copy of the signed Informed Consent will be given to the participants. The original signed form will be retained at the clinical investigation site.

## 5.5 Eligibility criteria

- 5.5.1 Inclusion criteria
- IDC-users (urethral or suprapubic), over 18, who have had a catheter in situ for at least one month and use a manual valve or drainage bag to collect urine
- Independent with catheter care needs (e.g. bag emptying or valve opening)
- Able to transfer from bed to chair, stand and walk short distances unaided
- Able to drink moderate levels of fluid (500mls in the first 2 hours and 150mls per hour thereafter)
- Able to provide informed consent (self-report and research nurse assessment)
  - Usual medical provider provides confirmation of suitability

#### 5.5.2 Exclusion criteria

- End stages of a terminal illness
- Current treatment of urinary tract infection
- Has been advised by a urologist against using a valve on clinical grounds
- Lack of bladder sensation (e.g. unable to sense when bladder needs emptying)
- Previous bladder surgery that could affect the integrity of the bladder
- At known risk of autonomic dysreflexia

## 5.6 Trial Procedures & Data Collection

There will be 2 groups of participants and the data collection process will be identical for both groups. Participants in both groups will undergo the following procedures (detailed in Flow charts in Appendix B and C):

# 5.6.1 Trial Procedures: Day 1 – Non-ambulatory testing

Pre-testing

- Confirm eligibility, answer any questions and ask participant to confirm consent (recorded on Day 1 Case report form).
- First drink (250mls) provided.
- Record demographic data on Day 1 Case report form (date of birth, address, telephone number, GP address).
- Take baseline observations and record on Day 1 Case report form: blood pressure, temperature, pulse and respiratory rate.
- Participant completes Quality of Life tools: EQ-5D-5L and Long-term Catheter Quality of Life Tool.

#### Testing Procedure

With the participant sitting (except when transferring to and lying on the bed for bladder scanning):

- 1. Participant puts on pad with pants to secure it in place
- 2. Record participant's self-reported bladder sensations
- 3. Scan bladder and record volume in Valve Log.
- 4. Research nurse fits the lowest pressure valve according to manufacturer's instructions for use and attach a drainage bag for urine collection. Record Valve Batch/Serial Number in Valve Log.
- 5. Record participant's self-reported bladder sensations in valve log
- 6. Scan bladder and record volume in valve log
- 7. If the valve remains open with urine draining freely, replace with the next level pressure valve (up to 3 valves) until free drainage has ceased and the valve remains closed. Record Valve Batch/Serial Number in Valve Log.

URINARY CATHETER 'FILL AND FLUSH' VALVE:

SAFETY, EFFECTIVENESS, ACCEPTABILITY AND FEASIBILITY TRIAL Protocol Version 3.1 20/08/2019 - IRAS: 245818 - ERGO: 41448

- 8. Participant to lie on bed for hourly bladder scanning (record time and volume in Valve Log) until bladder volume is >400mls or the participant experiences bladder discomfort or the valve automatically opens. Record participant's bladder sensations before each scan and:
  - a. If the volume is >400mls or the participant is experiencing discomfort
    - i. Ask the participant to contract abdominal muscles, press down on abdomen or bear down as if trying to pass urine to increase bladder pressure.
    - ii. If the valve opens, proceed as below (b).
    - iii. If the valve does not open, disconnect the valve, attach a new drainage bag and allow the bladder to drain. Stop the trial for that participant.
  - b. If the valve automatically opens:

Southampton

- i. Record the amount of urine voided
- ii. Scan the bladder for any residual volume
- 9. If the valve has opened with a urine volume of less than 500ml, repeat process 7 & 8 at 1 hourly intervals for 5 hours. If the valve did not open before bladder volume reached 500ml, stop testing at this point.

Participants will be requested to drink a minimum of 500mls of fluids over the first two hours, then a minimum of 150mls per hour for the next 3 hours. They will be given a choice of drinks. After testing has ended for that day, participants will be given a new manual valve and/or drainage bag as per usual use.

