## 3.2 The 'fill and flush' valve:

The fill and flush valve (Figure 1) is an automated valve which is designed to open in response to rising bladder pressure which occurs as the bladder becomes full. The valve is situated between the IDC and the drainage bag as a manual valve would be.

A detailed description of the valve is provided in the Clinical Investigator Brochure (CIB). Manufacturer's Part Numbers are as follows:

- EM02 Low Pressure Release
- EM03 Medium Pressure Release
- EM04 High Pressure Release

There are three variants of the valve which respond to different degrees of bladder pressure. People's bladders function at different pressure levels. One of the aims of this study is to gain preliminary data on which valve variant works and under which circumstances. Pressure ranges are as follows:

Low: 22 - 49cm H2O Medium: 35 - 61cm H2O High: 53 - 79cm H2O

Figure 1 Fill and Flush Valve

This valve is not currently CE marked and therefore an application has been made to the Medicines and Healthcare products Regulatory Agency (MHRA) for a Notice of No Objection to use it in this research study. The valve has shown promise for bladder drainage in preliminary laboratory studies using an experimental urinary tract (see section 3.5).

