#### 4.3 Outcomes

4.3.1 Primary outcomes:

Safety: Reliability

• Valve opening - Proportion of observations of automatic valve opening before bladder capacity (500ml or less) is reached - as measured by bladder scanner (Valve Log)

Safety: Effectiveness

- Bladder emptying proportion of valve voids with residual urine <100ml as measured by bladder scanner (Valve Log)
- Participant report (Valve self-report questionnaire) *Comfort*
- Participant report (Valve self-report questionnaire)

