## 5.9 Data Analysis:

5.9.1 Clinical

Descriptive statistics will be used to summarise

- Demographics of participants
  - Total number and percentage of men and women will be reported
  - Total number and percentage from each age groups will be reported
- Bladder volume when the valve opened and residual bladder volume when the valve closed while undertaking different activities
  - The range and mean average of the volume of urine in the bladder at each valve opening for each activity will be reported.
- Questionnaire findings (for each occasion the questionnaire is completed)
  - For binary questions (yes/no), the total number and percentage of each answer will be recorded
  - For scale response questions, the total and percentage number of participants answering each response (e.g. Very comfortable, Quite comfortable, neither comfortable or uncomfortable, Quite uncomfortable, Very uncomfortable) will be reported.

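### Day 1 reliability may mix unprovoked valve openings with openings set off by the scan transfer or by straining, because automatic opening is not defined by posture or trigger

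*Protocol*

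**What the plan says.** Protocol 5.6.1 titles Day 1 as non-ambulatory testing. Its Testing Procedure is carried out "With the participant sitting (except when transferring to and lying on the bed for bladder scanning"). Step 8 reads "Participant to lie on bed for hourly bladder scanning (record time and volume in Valve Log"), and step 9 says to "repeat process 7 & 8 at 1 hourly intervals for 5 hours" as long as the valve has opened below 500 ml. The entries named in the Day 1 steps are bladder sensations, valve number, time, scanned volume, voided amount and residual.

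Section 3.2 describes the valve as "designed to open in response to rising bladder pressure which occurs as the bladder becomes full". In step 8a, when the volume exceeds 400 ml or there is discomfort, staff are to "Ask the participant to contract abdominal muscles, press down on abdomen or bear down as if trying to pass urine to increase bladder pressure". If the valve then opens, step 8a.ii continues to (b), the branch headed by the valve opening automatically. Day 2 (5.6.2, step 19) has the same branch.

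The primary reliability outcome in 4.3.1 is "Proportion of observations of automatic valve opening before bladder capacity (500ml or less) is reached". Section 5.9.1 plans the following for opening volumes: "The range and mean average of the volume of urine in the bladder at each valve opening for each activity will be reported".

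**The concern.** The device that measures volume on Day 1 also disturbs the participant. Getting up, moving to a bed and lying down is physical effort, and the eligibility criteria (5.5.1) confirm that it is done without help: "Able to transfer from bed to chair, stand and walk short distances unaided". If that effort opens the valve, the opening belongs to the scan procedure and is not a response to filling alone. An opening obtained by asking the participant to strain is further still from an automatic one.

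Reliability is filed under safety in 4.3.1, and 3.4 names failure to open as a main risk. Counting provoked openings as automatic ones could hide some of the failures that this first-in-human study is meant to find. An opening also empties the bladder, so that fill can no longer show whether an undisturbed valve would have opened by 500 ml. If the trigger is not written down at the time, it cannot be recovered later.

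**Working it through.** The protocol gives no figure for this point, so there is nothing to reproduce. The check sets the text side by side and then shows how the proportion would respond.

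**1. Exposure.** Hourly scans for 5 hours (5.6.1, step 9) in 16 participants (5.3) give at most 16 × 5 = 80 hourly Day 1 scans. Each has a transfer to the bed. Scans at fitting and any residual scans that need a separate transfer would add to this.

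**2. Is an opening on transfer plausible?** The valve opens on pressure (3.2). Abdominal effort is used to raise pressure (step 8a.i). Standing is listed among the Day 2 ambulatory activities (5.6.2, step 18). The variant fitted first is the lowest-pressure one (step 4), with a range of 22 to 49 cm H2O (3.2), and it is replaced only if urine drains freely (step 7). The protocol's own logic therefore makes an opening on transfer possible. It gives no measured pressure for a transfer and no rate.

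**3. Would such an opening count?** The outcome in 4.3.1 has two conditions: automatic, and at 500 ml or less. Neither refers to posture or trigger. A transfer-time opening at, say, 300 ml meets both as written.

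**4. Would an opening on straining count?** Straining is requested once the volume is above 400 ml (or on discomfort), and the limit in the outcome is 500 ml. A strained opening between 400 and 500 ml meets the volume condition. Step 8a.ii then handles it in the automatic branch, and no stated rule keeps it out of the numerator.

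**5. Direction and size.** Treat each fill as one observation (an assumption). Let s be the proportion that would open unprovoked by 500 ml, and t the share of the remaining fills opened by a transfer. Then

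observed proportion = s + (1 − s) × t, and inflation = (1 − s) × t.

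Both s and t are assumptions; the documents support no value of either.

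| s | t | observed | inflation (percentage points) |
|---|---|---|---|
| any | 0 | s | 0 |
| 0.90 | 0.05 | 0.905 | 0.5 |
| 0.60 | 0.10 | 0.64 | 4 |
| 0.60 | 0.30 | 0.72 | 12 |
| 0.50 | 0.30 | 0.65 | 15 |

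The inflation cannot be negative. A fill that would have opened anyway stays a success; only a fill that would have failed can change. Over s = 0.50 to 0.90 and t = 0.05 to 0.30, the inflation runs from 0.5 to 15 points. With t = 0 it is nil.

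**The case against.** A reader might infer that the plan counts transfer openings as spontaneous seated ones and so overstates reliability at rest. The documents do not support that. They use neither term, and 4.3.1 sets no posture condition. The reference to rest in 4.2 belongs to the emptying objective, while reliability there means automatic opening within acceptable volumes. On that definition an opening during a transfer is not a miscount.

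Section 5.9.1 already plans to report opening volume by activity, which presupposes that activity is recorded somewhere. The Valve Log form and the Appendix B flowchart are not reproduced in the text available, and either may hold the field. Straining in step 8a is deliberate effort, so it is weak evidence about an ordinary transfer. The same sitting-and-transfer wording governs Day 2, so transfers are not peculiar to Day 1.

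All of this stands, and it rules out any statement that reliability is overstated. What remains is narrower. The outcome definition in 4.3.1 does not say how to classify an opening during a transfer or after straining, and the routing in step 8a.ii points the wrong way for a strict reading of automatic. Reporting by activity covers opening volume, not the primary proportion, and works only if transfer is one of the activities. A separate analysis plan could settle the counting rule, but it could not supply a trigger that was never logged.

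**Conclusion.** The point holds as a modest, inexpensive improvement. As written, the Day 1 reliability proportion may combine unprovoked openings (sitting or lying still) with openings set off by the scan procedure or by straining. Any bias in the unprovoked proportion is upward. Its size is unknown: 0.5 to 15 percentage points under the assumed ranges above, and nil if transfers never open the valve. The conclusion about transfers rests on the protocol's pressure logic, not on data. The conclusion about straining rests directly on the routing in step 8a.ii. If the Valve Log already has a posture or trigger field, the definition and the reporting rule are what remain to be settled.

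**What to change.** 1. Make sure the Valve Log records posture or activity and trigger at each opening on both days: sitting, transferring, lying still, deliberate straining, standing, walking, coughing.
2. In 4.3.1, define automatic as opening without deliberate straining, and align the wording of steps 8a.ii and 19a.ii so that strained openings are identified as such when recorded.
3. In 5.9.1, add transfer as its own activity category.
4. Report the primary proportion twice over the same denominator of all observations: once counting all automatic openings, and once with transfer-time openings not counted as unprovoked successes. List the fills ended by a transfer-time opening separately, as not assessable for unprovoked opening. For the fills observed, the two figures bracket the unprovoked proportion.

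Restricting the analysis to seated openings would not do the job. It discards openings while lying still, which are also unprovoked, and leaves the denominator undefined, because the seated outcome of a fill already emptied by a transfer cannot be observed.

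The cost is one log column, one extra activity row and a second proportion, with fewer fills assessable for unprovoked opening. The scan schedule, participant management and sample size do not change.
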